8.1.3. Exploratory (Part A) / Secondary (Part B) Efficacy Analyses

In this First-In-Patient study anti-tumor activity is an exploratory objective. The main analysis populations will be based on mITT and EP.

Tumor response, using RECIST, irRECIST, will be presented in the form of patient data listings which include, but are not limited to tumor response assessed in comparison to baseline. Traditional response measures in solid tumors, such as ORR and PFS were developed to evaluate chemotherapies and can be unreliable for tracking response to immunotherapies such as cancer vaccines. For example, apparent tumor burden may increase during the first few months of cancer vaccine treatment because of inflammation/T cell infiltration into tumors even in patients who go on to have durable responses. Time to progression and number of patients with progression could be calculated from first vaccination (Cycle 1 Day 1), but may also be calculated excluding those progressions that happened before some specific timepoints (eg, Day 57, Day 113). Time to response will be calculated from first vaccination (Cycle 1 Day 1) to time of first response (ie, CR or PR).

Additionally, total measurable tumor burden will be evaluated by the irRECIST criteria that include responses after disease progression that are not captured by RECIST evaluation criteria in solid tumors.

For tumor response data, the following analyses may be performed:

1. Tumor response (CR, PR, SD, PD, etc.) by cohort and visit, separately for RECIST 1.1 and irRECIST. Investigator provided tumor response will be presented by descriptive statistics (frequency and percentage).
2. Best overall response, by cohort, **across all available tumor assessments from both treatment period and maintenance period**, separately for RECIST 1.1 and irRECIST. Best overall response will be derived programmatically. In the tabular data presentation, a row of CR+PR will be added to show the results of ORR. With RECIST 1.1, tumor response (CR or PR) confirmation is optional as response rate is not the primary endpoint of the study, hence unconfirmed best overall response will be derived and presented. With irRECIST, tumor response (irCR or irPR) and disease progression (irPD) are required to be confirmed, however in this study tumor response confirmation is not required, therefore unconfirmed best overall response will be derived and presented. Descriptive statistics (frequency and percentage) will be provided.

Selected ad-hoc efficacy analyses (eg, ORR and radiographic PFS) combining participants from Cohorts 7A and 3B may be conducted, as participants in those two cohorts have identical or similar eligibility criteria for study entry and are scheduled to receive the same regimen.

Swimmer plots may be used to display duration of treatment and tumor response at each applicable time point. Waterfall plot for individual tumor size percent change from baseline, and spider plot for individual tumor size percent change from baseline over time may be presented. These plots, if generated, will be presented for RECIST 1.1 and irRECIST separately.

For the rPFS analysis in Part B, the Kaplan-Meier analysis may be performed if deemed necessary. If the Kaplan-Meier analysis is performed for radiographic progression-free survival, an event is defined as the first occurrence of “PD” status by investigator, or death, or a PCWG3 defined bone disease progression, whichever comes first, under RECIST. Time zero for all time-to-event analyses will be defined as the first vaccination on Cycle 1 Day 1. This analysis may be performed for the combined cohorts 7A and 3B. CCI

For duration of response per RECIST and time to response (from the first vaccination date to the time of the first response, CR or PR) in Part B, descriptive statistics will be provided. Kaplan-Meier analysis may be performed if deemed necessary. These analyses may be performed for the combined cohorts 7A and 3B.

PSA kinetics

PSA, PSA velocity, PSA slope and PSA doubling time (PSADT); PSA will be provided from laboratory data. PSA velocity is defined as the slope of the linear regression line of PSA against time in month. PSA slope is the slope of the linear regression line of natural log of PSA against time in month. PSA doubling time is defined as the natural log of 2 divided by the slope of the linear regression line of the natural log of PSA against time in month (see 10.2). These analyses will be conducted both for Central PSA and Local PSA in separate tables. PSA kinetics will be presented at individual level by timepoint (listings and plots). Mean % and absolute change from baseline in PSA kinetics may be presented by cohort. To report PSA-based outcomes, PCWG3 recommends that the percentage of change in PSA from baseline, as well as the maximum decline in PSA, PSA velocity, PSADT and PSA slope that occurs at any point after treatment be reported for each patient using a waterfall plot. Waterfall plots provide a broader and more sensitive display of data, and are more informative until a validated surrogate of clinical benefit is available.

A PSA-50 response rate may be calculated by cohort. PSA-50 response rate is defined as the proportion of patients whose on-study PSA declined from baseline by at least 50% at two consecutive measurements at least 3 weeks apart, prior to other systematic anti-cancer therapy. For the subset of PSA-50 responders, a duration of PSA-50 response will be summarized. Duration of PSA-50 response is defined as the period between the first

measurement when PSA-50 response was achieved to the measurement when PSA-50 response no longer holds.

Swimmer plots may be used to display duration of treatment and PSA values at each applicable time point.

CTC

The frequency of “traditional” and “all candidate” CTCs in whole blood each expressed as CTC/mL will be assessed in pre treatment (Screening, Cycle 1 Day 1) and post treatment (eg. Cycle 1 Day 71, Cycle 2 Day 1, Cycle 2 Day 29, Cycle 2 Day 99, and End of Treatment) samples. Analysis of the CTC endpoints may include absolute CTC and fold-change from baseline (pretreatment) by patient and % change and mean fold-change by cohort.

MDSC

The percentage of MDSCs will be assessed in pretreatment (Screening, Cycle 1 Day 1) and post treatment samples. MDSC levels will be presented per patient and per cohort by GMTs and GMFRs. Analyses of MDSC endpoints may include absolute and fold-change from baseline (pretreatment) by patient and % change and mean fold-change by cohort.

Bone scan assessment

Given the frequency of bone involvement in patients with progressive, castration-resistant disease, the decreased emphasis of early changes in PSA, and the increased availability of cytostatic agents, reliable methods to assess changes in bone are of increasing importance. PCWG3 recognizes that standards for using MRI and PET to assess bone metastases are under active investigation, so only radionuclide bone scans are considered here. PCWG3 also recognizes that there are no validated criteria for response on radionuclide bone scan.

[figure not shown]
For control/relieve/eliminate end points, the PCWG3 recommends that post-treatment changes be recorded simply as either “no new lesions” or “new lesions.” However, progression at the first scheduled assessment should be confirmed on a second scan performed 6 or more weeks later, in the absence of clearly worsening disease or disease-related symptoms. In the event of visible lesions disappearing, this should also be confirmed at the next scheduled assessment.

For prevent/delay end points, progressing disease on bone scan is considered when a minimum of two new lesions is observed. PCWG3 does not recommend performing a follow-up bone scan before 12 weeks of treatment unless clinically indicated. At the first 12-week reassessment, defining disease progression requires a confirmatory scan (which shows additional new lesions compared with the first follow-up scan) performed 6 or more weeks later, because lesions visible at the first 12-week assessment may represent disease that was not detected on the pretreatment scan. When further progression is documented on the confirmatory scan, the date of progression recorded for the trial, is the date of the first scan that shows the change.

Correlative analyses

Plots may be generated to display PSA kinetics vs. PSA antibodies (serology: Luminex assay). Similar plots may be generated to evaluate individual patient trends on MDSC, CTC and T-cell response.

CCI

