**DOCUMENT HISTORY**

Document	Version Date	Summary of Changes and Rationale
Amendment 8	29 May 2020	
Overall reasons for Amendment 8:
 
 
• Change in Study Design (Section 3): Cohort 3B will be reduced from 40 to 18 participants total.
 
 
Rationale: As regards the two cohorts with mCRPC, there is now sufficient sample size (n=33) to make an internal decision about further development of Pr Ca VBIR, based upon preliminary efficacy and safety. As such, there is no need to enroll additional participants.
 
 
• Change in Study Design (Section 3): Cohort 5B will be reduced from 40 to 15 participants total.
 
 
Rationale: Fifteen patients is considered a sufficient sample size to provide preliminary efficacy, safety, PK and biomarker data for the regimen.
 
 
• Change in Study Design (Section 3): Deletion of Cohort 10B.
 
 
Rationale: Studies of progression on novel-hormone therapy with abiraterone, with a switch to enzalutamide + Pr Ca VBIR, are no longer useful in defining Proof of Concept for this study.
 
 
• Deletion of inclusion criteria for Cohort 10B patients – Section 4.1.3.
 
 
Rationale: The combination of PrCa VBIR and enzalutamide will not be evaluated.
 
 
• Section 4.2 Exclusion criterion for COVID-19/SARS-CoV2 infection added.
 
 
Rationale: Guidance regarding COVID-19/SARS-CoV2 infection was required.

Document	Version Date	Summary of Changes and Rationale

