12. **Coagulation:** Should include Prothrombin Time (PT) or International Normalized Ratio (INR) and Partial Thromboplastin Time (PTT). Samples will be analyzed locally.
13. **Cardiac Troponin:** For participants undergoing screening, circulating levels of cardiac Troponin-I (cTnI) must be measured and found to be within the normal reference range within 28 days before study entry, preferably using the central laboratory kits provided. See [Section 7.1.7](#) for full details.
14. **Urinalysis:** Dipstick is acceptable. Microscopic analyses if dipstick abnormal. Samples will be analyzed locally.
15. **Triplicate 12 leads ECGs:** At each time point, three consecutive 12-lead ECGs will be performed approximately 2 minutes apart to determine mean QTcF interval. If the mean QTcF is prolonged (>500 msec), the ECGs should be re-evaluated by a qualified person at the institution for confirmation. Additional triplicate ECGs may be performed as clinically indicated.
16. **Registration:** Participant number and dose level allocation operated by Pfizer Inc.
17. **Investigational Product Administration:** Treatment to be administered after all other assessments required on that day have been performed.
18. **Tumor Assessments:** Tumor assessments will include all known or suspected disease sites. Screening images may be obtained within 5 weeks of registration. Imaging obtained as part of standard of care but within 28 days (-7 days) of registration may be used for screening assessment. Imaging may include chest, abdomen and pelvis CT or MRI scans or bone scans. Bone scans will be performed at baseline if disease is suspected and on-study as appropriate to follow disease. Baseline central nervous system (CNS) imaging is not required with the exception of symptomatic participants to rule out CNS metastases. CT or MRI scans, as well as bone scans, when indicated, are to be done every 8 weeks ( $\pm$  5 days) with the first one to occur 8 weeks after C1D1 until disease progression that requires new treatment modality, permanent discontinuation, or death. Disease progression will be confirmed with two consecutive timepoints at least 4-6 weeks apart in the absence of rapid clinical deterioration. Tumor assessment should be repeated at the End of Treatment visit if more than 6 weeks have passed since the last evaluation. **CCI** [REDACTED]  
[REDACTED]  
[REDACTED]

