### **3.1.2. Dose Expansion (Part B)**

In Part B, the selected doses of the PrCa VBIR in combinations with PF-06801591 were evaluated in two populations: (1) Participants with mCRPC whose disease has progressed despite novel hormone therapy (abiraterone or enzalutamide) to be treated with PrCa VBIR+ PF-06801591 alone; and (2) Participants with biochemical relapse of disease (BCR) to be treated with PrCa VBIR+ PF-06801591.

The study design has changed in two aspects: (1) in the removal of Cohort 10B, because studies of progression on novel-hormone therapy with abiraterone, with a switch to enzalutamide + Pr Ca VBIR, are no longer useful in defining Proof of Concept for this study; and (2) in no longer expanding cohort 3B, because sufficient sample size has been reached to make decisions about further development based upon safety and preliminary efficacy.

The following listing identifies the Expansion Cohorts for Part B:

- Cohort 1B (20 participants treated): Twenty participants with BCR have been enrolled and treated in this expansion cohort, using PrCa VBIR and tremelimumab at a dose level of 80 mg. No PF-06801591 was included in this regimen. **No additional participants will be enrolled.**
- Cohort 5B (15 participants treated): Fifteen participants with BCR and no prior therapy have been treated with PrCa VBIR in combination with 130 mg PF-06801591. **No additional participants will be enrolled.**
- Cohort 3B (18 participants treated): Eighteen participants with mCRPC whose disease has progressed despite novel hormonal treatment (enzalutamide or abiraterone) have been treated with PrCaVBIR in combination with 300 mg PF-06801591. **No additional participants will be enrolled.**

Different cohorts of patients opened for enrollment in parallel. Cohorts are non-randomized; slot assignments were managed by the study team with sites notified in advance of cohort availability. Participants are not allowed to crossover between the different combinations evaluated in this study.

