### **9.3. Sample Size Determination**

The exact sample size of the 3+3 designs in the Phase 1 Part A (Dose Escalation) cannot be pre-specified because of the dynamic feature of the design. The number of patients to be enrolled in the study will depend upon the observed safety profile, which will determine the number of patients at each dose level (eg, 3 or 6) and the number of dose levels explored.

Typically, at least 3 patients will be treated at each regimen dose level. Dose cohorts with an acceptable safety profile (0/3 or 1/6 patients with DLTs) may be expanded up to N=15 to further assess safety, immune response, pharmacokinetics, and pharmacodynamics. Decisions to enroll additional patients at dose levels already cleared for safety will be based on clinical judgment of the investigators and the sponsor considering all evaluable safety, immunoresponse, and/or pharmacodynamics data.

The estimated sample size for Part A would be 24-48 patients and will be dependent on the safety profile observed.

The sample size for Cohort 1B (AdC68 + pDNA + treme 80 mg SC for BCR patients who had no prior therapy) was determined clinically rather than statistically. Twenty patients were enrolled in that cohort to provide preliminary efficacy, safety, PK and biomarker data for this regimen.

For Cohort 3B (AdC + pDNC + treme 80 mg SC + PF-0689159 300 mg SC. for patients with mCRPC whose disease has progressed despite novel hormonal treatment), 18 patients were enrolled. The sample size was determined clinically rather than statistically. The smaller sample size was determined to be adequate for continued safety analysis. The main efficacy endpoint for this cohort will be objective response rate (ORR) based on RECIST version 1.1. There are no hypothesis tests for these endpoints. Bayesian approach with a non-informative

Jeffery's prior beta (0.5,0.5) will be used to calculate the posterior probability the ORR of the study treatment exceeds various ORR thresholds of interest in the end of the study. For example, if 6 responders were observed in the 18 patients, the posterior probability that the true ORR is greater than 25% would be about 80%.

For Cohort 5B (AdC68 + pDNA + treme 80 mg SC + PF-0689159 130 mg SC. for BCR patients who had no prior therapy), the sample size was determined clinically rather than statistically. Fifteen patients were enrolled in that cohort to provide preliminary efficacy, safety, PK and biomarker data for the regimen.

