#### 9.4. Efficacy Analysis

CCI

The main

analysis populations will be based on mITT and EP (see Section [Analysis Sets](#)).

Tumor response, using RECIST v1.1, irRECIST, and PCWG3 for bone disease, will be summarized and presented in the form of patient data listings. Traditional response measures in solid tumors, such as ORR and PFS were developed to evaluate chemotherapies and can be unreliable for tracking response to cancer vaccines. For example, apparent tumor burden may increase during the first few months of cancer vaccine treatment because of inflammation/T cell infiltration into tumors even in patients who go on to have durable responses. For these reasons time to progression and number of patients with progression could be calculated from first vaccination (Day 1), but also calculated excluding those progressions that happened before some specific timepoints (eg, Day 57, Day 113). Time to response will be calculated from first vaccination (Day 1) to time of first response (ie, CR or PR). When PFS is evaluated, the Kaplan-Meier approach will be used. Participants from Cohorts 7A and 3B may be combined for efficacy analyses as participants in those two cohorts have identical or similar eligibility criteria for study entry and are scheduled to receive the same regimen.

Additionally, total measurable tumor burden will be evaluated by the irRECIST criteria that include responses after disease progression that are not captured by RECIST evaluation criteria in solid tumors.

The Bayesian analyses as described in [Section 9.3](#) will be carried out separately and may not be reported in the clinical study report.

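### The optional recalculation that leaves out early progressions has no handling rule; if those participants are dropped or censored it can only flatter the result, materially so at a Day 113 cut-off

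*SAP*

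**What the plan says.** SAP 8.1.3 provides for time to progression and number of patients with progression from first vaccination, "but may also be calculated excluding those progressions that happened before some specific timepoints (eg, Day 57, Day 113". Protocol 9.4 has the parallel sentence: "but also calculated excluding those progressions that happened before some specific timepoints (eg, Day 57, Day 113". The SAP's reason is that "apparent tumor burden may increase during the first few months of cancer vaccine treatment" because of inflammation, even in patients who later respond durably.

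The surrounding text sets the context:

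- **Clock.** SAP 8.1.3: "Time zero for all time-to-event analyses will be defined as the first vaccination on Cycle 1 Day 1". It is not moved to the cut-off.
- **Scans.** Every 8 weeks, plus or minus 5 days, "with the first one to occur 8 weeks after C1D1" (protocol Schedule of Activities, tumor assessment footnote).
- **Handling.** Neither document says whether a participant with an excluded progression is dropped, censored at that date, or followed to the next progression. SAP 10.3 defers PFS and rPFS censoring rules to a programming specification.
- **Status.** Both versions are optional in the SAP and neither is named main. SAP 4.1 plans no hypothesis tests.
- **Part B rPFS.** SAP 8.1.3 counts the first progression, death or bone progression and states no early exclusion.
- **Design.** "Cohorts are non-randomized" (protocol 3.1.2). For Cohort 3B, "18 patients were enrolled. The sample size was determined clinically rather than statistically" (protocol 9.3).

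**The concern.** The exclusion works by date alone. It removes an early progression that is later confirmed as readily as one that proves to be inflammation. With the clock left at Day 1, a participant counted after the cut-off carries the whole pre-cut-off period as progression-free time, while those who failed in that period no longer count as failures. That is guarantee-time bias.

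In a randomized comparison both arms would carry the same exclusion. Here there is no control arm, so a reader cannot separate the arithmetic gain from drug effect. Preliminary efficacy is also put to use: the Amendment 8 rationale says of the mCRPC cohorts that "there is now sufficient sample size (n=33) to make an internal decision" on further development, and protocol 3.1.2 gives safety and preliminary efficacy as the basis for such decisions. Because the cut-off and the handling are open and SAP section 3 has the sponsor's team reviewing data throughout, both could be settled after results are seen.

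**Working it through.** The documents give no median, event count or power for time to progression, so there is no planned figure to reproduce.

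**1. Direction.** Let *c* be the cut-off, *n* participants, *e* progressions, *k* of them before *c*. If the *k* participants are dropped or censored, every Kaplan-Meier factor before *c* becomes 1 and later risk sets are unchanged:

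- S_excl(t) = S(t) / S(c−) ≥ S(t) for t ≥ c.
- The count falls from e to e − k. The proportion becomes (e − k)/(n − k) if dropped or (e − k)/n if censored; neither exceeds e/n.

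With k = 0 nothing changes.

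**2. What each cut-off catches.** Scans fall on nominal Day 57 (window Day 52 to 62) and Day 113 (window Day 108 to 118). Among scheduled scans, before Day 57 catches only Days 52 to 56. Before Day 113 catches the whole first scan plus Days 108 to 112 of the second.

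**3. Direct calculation, Day 113.** Assumptions: exponential time to progression, true median m of 2, 4, 6 or 12 months of 30.4375 days, scan days uniform in the window (so 5/11 of second scans precede Day 113), no dropout. S(x) = 2^(−x/m), with x in days after Day 1. S(113−) = S(56) − (5/11)[S(56) − S(112)]. The third scan (Day 164 to 174) precedes Day 180, so the Day 180 rate is S(168).

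| m (months) | S(56) | S(112) | S(113−) | Removed of 18 | Day 180 rate, full | Day 180 rate, excluded |
|---|---|---|---|---|---|---|
| 2 | 0.529 | 0.279 | 0.415 | 10.5 | 0.148 | 0.356 |
| 4 | 0.727 | 0.529 | 0.637 | 6.5 | 0.384 | 0.603 |
| 6 | 0.809 | 0.654 | 0.738 | 4.7 | 0.529 | 0.716 |
| 12 | 0.899 | 0.809 | 0.858 | 2.6 | 0.727 | 0.847 |

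Removed = 18 × [1 − S(113−)]. The last column is S(168)/S(113−).

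**4. Simulation, Day 113, n = 18.** 1,000 runs per setting, the same scan schedule, 15% per year random dropout, finite follow-up, no drug effect modelled; early progressors dropped or censored.

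| m (months) | Mean number progressing | Kaplan-Meier median (day) | Progression-free at Day 180 |
|---|---|---|---|
| 2 | 17.0 → 6.7 | 62 → 168 | 14% → 34% |
| 4 | 15.1 → 8.9 | 164 → 224 | 38.1% → 59.4% |
| 6 | 13.0 → 8.4 | 221 → 282 | 52.2% → 71.0% |
| 12 | 8.6 → 6.1 | 390 → 398 | 72.3% → 84.5% |

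The Day 180 gain is 12 points (84.5 − 72.3) to 21 points (59.4 − 38.1). No run gave a shorter median or more progressions. With n = 33 and 4 months: 27.6 → 16.0 progressions, Day 165 → 225.

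Two medians need care. At 2 months, S(56) = 0.529 is so close to one half that the full-analysis median falls in either the first or the second scan window; at n = 33 it is Day 108 → 169. At 12 months, 390 → 398 understates the shift, because with limited follow-up the excluded curve often does not reach 50%. Directly, the first nominal scan with S ≤ 0.5 is Day 393 (S(392) = 0.475). With the exclusion S must fall to 0.5 × 0.858 = 0.429, which is Day 449 (S(448) = 0.427). That is one scan interval of 56 days.

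**5. Day 57, n = 18.** Mean progressions 17.0 → 13.3, 15.1 → 13.0, 13.0 → 11.4 and 8.8 → 8.0. The median moves about 3 to 6 days and the Day 180 rate rises 4 to 5 points. In 1%, 10%, 20% and 45% of runs no progression preceded the cut-off and nothing changed.

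**6. Other reading: ignore the early progression and count the next.** The count was unchanged in 71% to 98% of n = 18 runs (4 months, Day 113: 15.1 → 14.9) and the Day 180 rate was essentially unchanged. The Day 113 median hardly moves at 4 months (164 → 170) and not at 6 or 12. It was slightly shorter in 0.2% to 5% of n = 18 runs. At 2 months it can still move (n = 33: 108 → 166), because early events are deferred past the cut-off.

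**The case against.** The strongest defence is that this is a disclosed, optional extra with a clinical reason. It is descriptive and untested; SAP 4.3 makes ORR the main and rPFS the key supportive efficacy endpoint for Cohort 3B; Part B rPFS has no such exclusion; and patient listings keep early progressions visible. All of that stands and limits the weight of the point.

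Three stronger readings are tempting, and the documents do not support them:

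- **That the exclusion guarantees a longer time and fewer progressions.** The text excludes progressions, not participants. Protocol 3.1 encourages treatment for at least 24 weeks despite progression, so counting the next progression is a possible reading, and under it the effect largely disappears. Under any reading nothing changes if no progression precedes the cut-off.
- **That the excluded figure will drive the development decision.** The documents say preliminary efficacy informs that decision; they do not say this version would be used or reported as the headline.
- **That irRECIST already covers the purpose, so the analysis should be deleted.** Protocol Appendix 4 bases irRECIST on target and measurable lesions, while protocol 4.1.2 requires a measurable lesion in only about 40% of Part B mCRPC participants. irPFS cannot replace a late-effect view for the rest.

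What the defence does not answer is that cut-off, handling and main analysis are all left open.

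**Conclusion.** The point holds in a limited form. When early progressors are dropped or censored, the recalculated result is never less favourable than the full one, for reasons unrelated to treatment. At Day 113 the effect is material across assumed true medians of 2 to 12 months: the Day 180 rate gains about 12 to 21 points and the median moves by roughly one scan interval or more. At Day 57 it is small. The sizes rest on exponential progression, the planned scan schedule and an assumed median; the absolute counts also depend on follow-up length. The direction rests on none of these, only on the drop-or-censor reading. The plan should be changed because the study is uncontrolled and the handling is undefined, not because a primary result is at risk.

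**What to change.** In SAP 8.1.3 and protocol 9.4:

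1. Name the unexcluded analysis from Cycle 1 Day 1 as the main one and commit to reporting it whenever any variant is shown.
2. Replace the date-based exclusion with a landmark analysis at one fixed cut-off: participants alive, progression-free and in follow-up at the landmark, time counted from the landmark, with the number excluded and the reasons shown. Days 57 and 113 both sit inside a scan window, so state how scans within the window are assigned.
3. Label it a sensitivity analysis, not for comparison with outside benchmarks.
4. Present it alongside irPFS for participants with measurable disease and PCWG3-confirmed bone progression.

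The cost is wording in two sections and one reworked optional analysis, with no new data. Its figure may be less favourable than the one the present text allows, and a landmark analysis describes only those who reach the landmark.
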